**Development and Evaluation of a Health Literacy-Informed Communication Intervention for Discharge
Medication Counseling in Hospitalized Children**

Principal Investigator

[name]

Pediatric Hospital Medicine Fellow

Department of Pediatrics

Monroe Carrel Jr. Children's Hospital at Vanderbilt
Vanderbilt University Medication Center

Co-Investigators

[name] MPH

[name], MSPH

Table of Contents:

- 1.0 Background**
- 2.0 Rationale and Specific Aim**
- 3.0 Study Design, Study Population, Statistical Analysis and Sample Size Calculation**
- 4.0 Risk to Participants**
- 5.0 Privacy/Confidentiality Issues**
- 6.0 Reporting of Adverse Events or Unanticipated Problems Involving Risk to Participants**
- 7.0 References**

Protocol Summary

Caregivers of children age \leq 6 years old who speak English or Spanish and are discharged home from the inpatient hospital medicine team at Monroe Carell Jr. Children's Hospital at Vanderbilt on a new liquid medication will be potentially eligible for the study. Caregivers will be randomized at the time of enrollment to receive usual care for discharge medication teaching or receive enhanced discharge medication teaching which is a health literacy-informed communication intervention including a written medication sheet, teach-back, provision of an oral dosing syringe and show-back of proper liquid medication administration. Caregivers will be enrolled in person prior to their child's discharge home from the hospital. A follow-up survey conducted via myCap will be completed 48 to 72 hours following discharge to assess study outcomes. The anticipated study duration is 2 years total of which 12 months is anticipated for subject recruitment and enrollment starting July 1, 2021.

1.0 Background

One out-of-hospital medication error occurs every 8 minutes among children $<$ 6 years of age.¹ Medication errors are particularly common in infants and young children, likely due to the near universal use of liquid medications in this population. As compared to pills or tablets, oral liquid medications present unique challenges (e.g., varying concentrations, dose measurement, and the frequent use of non-standardized dosing instruments) and account for the majority of pediatric dosing errors. Prior studies estimate that liquid medication dosing errors in children are very common with over 50% of caregivers measuring an incorrect dose or reporting giving a dose outside of the recommended range.²⁻⁶ Poor medication adherence (e.g. missed doses) further compounds the problem of medication errors in children with potential implications for treatment failure and, in the case of antibiotics, development of drug resistance.^{7,8}

More than 1.5 million children are hospitalized in the United States each year, and the transition from hospital to home is a vulnerable time for medication errors.⁹ Most children receive multiple medications during a hospital stay.¹⁰ Many of these medications are new and many are continued at home. This raises the risk for errors as the responsibility of medication administration shifts from trained health care providers to caregivers, many of whom experience increased stress and exhaustion during a hospitalization making comprehension of medication instructions more difficult.

Health literacy, or the ability to understand health information to make appropriate health decisions, is a key driver of effective communication, especially when discussing medication administration.¹¹ Low health literacy is common, present in 29% of US parents, and is associated with increased risk of medication errors.¹¹ It is thus imperative to consider health literacy as a critical element of effective communication with caregivers in the transition from hospital to home in order to minimize medication errors. Several studies in outpatients have demonstrated the usefulness of health literacy-informed communication strategies (written instructions, teach-back, show-back) for reducing medication errors.¹²⁻¹⁴ Evaluations of health literacy-informed communication interventions calibrated to the unique complexities and needs of caregivers in the transition from hospital to home, however, are lacking.

2.0 Rationale and Specific Aim

Despite the association of poor health literacy of caregivers with worse health outcomes in children, actual caregiver health literacy has been assessed in only 5 emergency department studies and no inpatient studies which examined medication errors.^{13,15-18} Addressing health literacy is integral to any proposed solution seeking to eliminate out-of-hospital medication errors as children transition from the hospital to home. Given the exhaustion and stress of a hospitalization, all caregivers are at risk to perform below their normal level of health literacy. Therefore, healthy literacy “universal precautions” should be followed by all health care workers which means assuming that all patients and caregivers may have difficulty comprehending health information.¹⁹ The Joint Commission has stated that unaddressed health literacy issues undermines the safety of patients, and health care organizations must identify and meet patient's oral and written communication needs.²⁰ Ways to meet these needs and improve medication safety include using proven communication strategies, such as teach-back, show-back, and providing written information.^{21,22} Use of pictograms along with written instructions is associated with improved comprehension and adherence with medical instructions,

especially in those with low health literacy.^{2,14,23,24} Unfortunately, standardization and utilization of proven communication strategies in the hospital is often poor.^{21,25}

Prior work has highlighted the commonality of liquid medication errors in infants and young children and the potential of enhanced communication strategies to reduce errors, resulting in care that is safer and more effective. However, few studies have examined health literacy-informed interventions to decrease discharge liquid medication administration errors and improve medication adherence in hospitalized children during the transition from hospital to home. Our proposed study directly addresses this important knowledge gap.

The overarching goal of this research is to make post-discharge care for children safer and more effective. Our objective is to 1) design and test the efficacy of a health literacy-informed discharge medication counseling intervention in the inpatient setting to reduce medication dosing errors by caregivers and improve adherence in infants and young children discharged home on a liquid medication. The specific aim of this study is:

Specific Aim *In a randomized controlled trial, we will test the efficacy of a health literacy-informed communication intervention on caregiver discharge medication dosing accuracy, adherence, and comprehension. We hypothesize that a useable, health literacy-informed medication counseling intervention will be efficacious in reducing liquid medication dosing errors and improve adherence and medication comprehension among caregivers following hospital discharge for children receiving liquid medication as compared to usual care.*

The primary outcome is observed dosing accuracy assessed via picture of an oral dosing syringe submitted by a caregiver 48-72 hours following discharge and compared to the prescribed dose in the chart. The primary outcome will be a continuous measure of percent difference of the caregiver submitted photo compared to the prescribed dose (in mL). The primary measure will also be assessed as a dichotomous variable as +/- 20% from the prescribed dose. Secondary outcomes include caregiver medication adherence and medication comprehension assessed via caregiver follow-up survey.

3.0 Study Design, Study Population, Statistical Analysis and Sample Size Calculation

3.1 Study Design and Study Population

We will conduct a randomized controlled trial (RCT) over a period of 12 months among English- and Spanish-speaking caregivers of children age birth to \leq 6 years being discharged from the hospital following an acute care inpatient stay in which at least one new liquid medication is initiated to be continued at home. Inclusion and exclusion criteria are outlined in Table 2. In addition, we will only include caregivers who will be or have already obtained their child's medicine from the Vanderbilt Children's Outpatient Pharmacy and are willing to download and use an application on their phone called myCap to complete the follow-up survey.

Table 2. RCT inclusion and exclusion criteria

[figure not shown]
Inclusion Criteria	Exclusion Criteria
Caregivers of children from birth to $<$ 4 years	Medications administrated by home health nurse
English or Spanish speaking	Caregiver not fluent in English or Spanish
Discharged on a new scheduled liquid medication for a minimum duration of at least 3 days	Child in state custody (i.e., Department of Child Services)

3.2 Screening and Enrollment

Caregivers will be screened for eligibility Monday through Friday from 7 am to 6 pm. The PI or trained research assistant(s) will review currently admitted patients on the general hospital medicine teams who meet eligibility criteria and contact the attending physician to inquire about discharge status and request permission to approach the caregiver. For patients nearing discharge, caregivers will be approached to discuss the study and confirm eligibility (see Interest in Participation Script). An eligibility script will be used to standardize this process (see included document) Patient-level randomization will occur at the time of enrollment. Allocation to intervention or usual care will be done by block randomization and will be assigned when individuals are determined to be eligible based on the eligibility script. Due to the nature of the intervention, it will not be possible to blind study staff or caregivers to the assigned study arm (intervention or usual care).

At the time of enrollment (i.e., either the day prior to discharge, if possible, or the day of discharge), caregivers in both groups will complete a demographics questionnaire via a secure web platform called REDCap (Research Electronic Data Capture).²⁶ Questions will include patient (child) age, sex, race/ethnicity, whether they were receiving any liquid medication prior to admission, number of previous hospitalizations, and number of previous daily medications. Demographic questions about caregivers will include age, gender, race/ethnicity, education level, caregiver relationship to patient, marital status of caregiver, education level of caregiver, employment status, difficulties paying bills (proxy for financial stress), country of origin, and preferred language. The following information will be extracted from the electronic health record: child discharge diagnosis, medication(s) name, number, frequency, dose and duration of discharge medication(s), patient insurance status, and number of chronic conditions.²⁷ Caregiver health literacy will be measured using the Newest Vital Sign (see included document).²⁸ The Newest Vital Sign has been translated into Spanish by the creators. See Figure 1 for study flow.

[figure not shown]
Figure 1. Aim 2 Study Flow

3.3 Intervention

Intervention: The design of the medication instruction sheet was guided by previous research, our previous qualitative study (IRB#201452), and work by Yin et al.¹⁵ The medication instruction sheet will include a pictogram of a syringe marked with the correct dose of medication as well as information about the dose frequency, route of administration, length of treatment, storage and most common medication side effects (see example medication instruction sheet). The medication instruction sheets will be customized for each patient based on the discharge medicine, printed and used to facilitate discharge medication counseling which will include demonstration of accurate dosing with a standardized instrument (i.e., dosing syringe) by research staff followed by caregiver “show-back” of how they plan to administer the medication at home and “teach-back” regarding dosing amounts, times and end dates of medications and common side effects. This will be standardized within an intervention script (see included document) and will be piloted prior to implementation. A clear dosing syringe will be provided to the family prior to discharge. The syringe will be the smallest syringe that would allow administration of the appropriate dose. Caregivers will be given the instruction sheet to use at home. If children receive more than one liquid discharge medication, the intervention will be completed for only one randomly selected medication. We anticipate the intervention will take approximately 10 minutes. We anticipate that the eligibility screening, initial survey and intervention will take approximately 25 minutes to complete.

Usual Care: Caregivers in the usual care group will receive standard of care discharge communications per unit routine, including counseling regarding prescribed medications and post-discharge instructions, return precautions, and follow-up appointments by the pediatric nursing staff. At our institution, children discharged with a liquid medication from our outpatient pharmacy are provided with a dosing syringe as part of routine care. All communications about discharge medication instructions will be at the discretion of the clinical team as part of routine care. An additional dosing syringe will be supplied in a sealed envelope to be used at the discharge follow-up visit in order to standardize the assessment of the primary outcome of observed dosing accuracy.

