3.4 Assessment of Outcomes

Follow-up Survey via myCap: The follow-up survey will be completed 48 to 72 hours following discharge to assess study outcomes. This will be done via myCap. myCap is an application that research participants will be asked to download on their phones (application is free and available on iPhone and Android phones). myCap leverages REDCap to capture participant/patient reported outcomes via mobile devices. myCap is HIPPA-compliant and secure. All data collected via myCap converts results into a format compatible with REDCap. The primary outcome of dosing accuracy will be assessed along with secondary outcomes (medication adherence and medication comprehension) via surveys in myCap. Caregivers will also be asked who administered the medication, what kind of teaching they received in the hospital prior to discharged (i.e., did teach-back, show-back occur), whether any serious medication errors occurred with the patient or other children in the home and/or if there were unplanned visits to a health care provider (see included follow-up survey). Caregiver self-efficacy for administering medicines to their children will be assessed using a standardized scale called the Medication Understanding and Use Self-Efficacy Scale (MUSE). See included document for RCT follow-up survey. We anticipate that the caregiver follow-up survey this will take <15 minutes to complete.

Primary Outcome: Dosing accuracy will be the primary outcome and will be assessed through self-report (reported dose) and through observation (observed dose) at follow-up. The primary outcome will be *observed dosing accuracy*. For *observed dosing accuracy*, caregivers will be asked to draw up a dose of their child's medication using the provided oral dosing syringe and send a secure picture of the syringe via myCap to research study staff (see Figure 2 as an example). The primary outcome will be assessed as a continuous percent difference from the prescribed dose (in milliliters). For *reported dose*, caregivers will be asked to report the prescribed volume (in milliliters) of medication to be given with each dose during the follow-up myCap survey. This will be compared to the prescribed dose in the electronic medical record. For both measures, dosing accuracy will also be assessed as a dichotomous outcome and considered accurate if it is within 20% of the prescribed dose similar to prior studies.^{5,15}

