3.5 Data Analysis and Sample Size

Data analysis: Baseline characteristics of the intervention and control groups will be compared using *t* tests and χ^2 tests or Fisher exact tests, as appropriate. Wilcoxon rank-sum tests will be used if the data does not appear to be normally distributed. These tests will be performed to also compare those who did and did not complete the follow-up assessment.

Randomization will be done using block permutation at the time of enrollment. Study staff enrolling caregivers will not be blinded to group allocation. Caregivers will not explicitly be told what group they have been assigned. Study staff will be blinded to group allocation when assessing the dose in the syringe in the picture submitted during follow-up in order to determine the primary outcome of observed dosing accuracy. Two independent study staff will assess the picture to determine the dose. Any disagreement will be adjudicated by the study PI.

The primary outcome will be the percent difference in the observed dose measured as the difference in millimeters (mL) between the dose of medication in the caregiver submitted picture during follow-up assessment compared to the prescribed dose in the electronic health record divided by the prescribed dose. For example, if the observed dose in the caregiver submitted picture was 4.5 mL and the prescribed dose in the electronic health record was 3 mL then this would be a 50% overdosing error. The observed dosing percent difference will be compared between the intervention and control groups as medians with interquartile ranges.

Last Revision: 4/21/2022

Table 4. Demographics of potentially eligible children, July 2018-June 2019 (N = 1,742)

Characteristic	N (%)
Age (y)	
0 to < 6 months	940 (54)
6 mos to <1yrs	183 (11)
12 mos to < 2 yrs	288(16)
2yrs to < 3yrs	205 (12)
3yrs to < 4 yrs	125 (7)
Sex	
Male	958 (55)
Female	784 (45)
Race/Ethnicity	
Non-Hispanic white	1098 (63)
Non-Hispanic black	244 (14)
Hispanic	296 (17)
Other	104 (6)

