If we detect covariate imbalance in the two groups, we will use propensity score weighting and a multivariable linear regression model to conduct an adjusted analysis. Proposed covariates to include in the model are: caregiver health literacy, caregiver age, caregiver gender, caregiver race/ethnicity, and caregiver primary language. These covariates are likely to have the biggest impact on the primary outcome. The other covariates includes caregiver country of origin, socioeconomic status (i.e., binary outcome of do you have difficulty paying bills), employment status, education status, and marital status. Patient level covariates include child age, gender race/ethnicity, medical complexity, number of previous medications and previous hospitalizations in the last year and insurance type.

We will display our findings for the continuous outcome of observed medication dosing error using either box plots or violin plots for the intervention and control groups.

Given that prior literature in this area has examined medication dose error as a dichotomous variable using +/- 20% from the prescribed dose (this was felt to be a clinically meaningful dosing error), we will also examine and display our primary outcome in this way to allow for comparison to other studies. We will report relative risk reduction, absolute risk reduction and number needed to treat along with 95% confidence intervals for the primary outcome of both observed dosing accuracy and reported dosing accuracy.

Sample Size: Sample size estimates are based on the outcome of medication dosing accuracy. Using a conservative dosing error prevalence of 30% in the control arm,^{2,4-6,15} and an expected dosing error prevalence of 10% in the intervention arm, we will need to enroll 72 subjects in each arm of the study to reject the null hypothesis that the dosing error prevalence in the control and intervention arms are equal with 80% power (2-sided alpha of 0.05). Accounting for 25-30% loss to follow-up, we plan to enroll a total of 200 subjects. From July 2018-June 2019, the pediatric hospital medicine service at Vanderbilt discharged 1,742 children <4 years of age, at least 50% of whom were discharged home on 1 or more medications (approximately 75 children per month), ensuring ample opportunities to achieve our required sample size (see Table 4).

3.6 Potential Limitations and Alternative Approaches for Aim 1

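### For doses close to the syringe's capacity, one picture of one fill cannot show an overdose above 20%, at least in the intervention arm; fills are not counted and the usual-care syringe size is not stated

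*Combined protocol and SAP*

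**What the plan says.** Section 3.3, Intervention paragraph, on the syringe given to the family: "The syringe will be the smallest syringe that would allow administration of the appropriate dose".

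Section 3.3, Usual Care paragraph: "An additional dosing syringe will be supplied in a sealed envelope to be used at the discharge follow-up visit". Its stated purpose is "in order to standardize the assessment of the primary outcome of observed dosing accuracy". No size is given for it.

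Section 3.4, Primary Outcome: "caregivers will be asked to draw up a dose of their child's medication using the provided oral dosing syringe", and they then "send a secure picture of the syringe via myCap to research study staff". Section 3.5 adds: "Two independent study staff will assess the picture to determine the dose".

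The primary outcome is the percent difference from the prescribed volume, summarised in section 3.5 as medians with interquartile ranges. The scoring example supposes that "if the observed dose in the caregiver submitted picture was 4.5 mL and the prescribed dose in the electronic health record was 3 mL", a 50% overdose. Section 3.5 also treats "medication dose error as a dichotomous variable using +/- 20% from the prescribed dose" and attaches to it the relative risk reduction, absolute risk reduction and number needed to treat. The sample size (30% versus 10% error, 72 per arm) uses error prevalence, that is, the dichotomous form.

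The protocol text describes no second fill, second picture, code for a full syringe or minimum capacity above the dose.

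**The concern.** The sizing rule brings the syringe's capacity as close to the correct dose as the stock allows. That suits teaching, but the same device is then the measuring instrument, and its upper range may end inside the band that counts as accurate. Underdoses are not limited in this way, so the loss is one-sided.

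A caregiver who means to give more than the syringe holds has to refill it. One picture then shows either a full syringe, which for a dose near capacity reads as accurate, or the second partial fill, which reads as an underdose. For example, 4.5 mL given from a 3 mL syringe leaves a second fill of 1.5 mL, scored as −50% against a 3 mL prescription.

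If the usual-care envelope syringe follows a different sizing rule, the limit differs by arm and can lower the intervention arm's recorded error rate. If it follows the same rule, both arms lose true errors. The safety follow-up in section 3.4 is also triggered by the picture or the survey, so an overdose that the picture hides is left to the survey to detect.

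**Working it through.** **Limit of the instrument.** Let D be the prescribed volume and C the syringe capacity. Assuming that the syringe cannot be read materially past its top mark, the largest overdose one fill can show is (C − D)/D. A reading above +20% needs C > 1.2 × D. It is therefore impossible when D ≥ C/1.2 = 0.833 × C.

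**The plan's example.** A picture of 4.5 mL against 3 mL needs C ≥ 4.5 mL. Under the section 3.3 rule it can arise only if no stocked syringe holds from 3 mL to just under 4.5 mL. The stock is not given.

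**Share of doses capped (sizes and dose mix assumed).** Doses spread evenly over 0.5–10 mL, a span of 9.5 mL:
- Sizes 1, 3, 5, 10 mL: blocked intervals 0.833–1, 2.5–3, 4.167–5 and 8.333–10. Total 0.167 + 0.5 + 0.833 + 1.667 = 3.167; 3.167/9.5 = 33%.
- Sizes 1, 3, 6, 12 mL: 0.167 + 0.5 + 1.0 = 1.667 (the 12 mL interval begins at 10 mL); 1.667/9.5 = 18%.
- Sizes 1, 3, 6, 10 mL: 3.333/9.5 = 35%.
- 10 mL only: 1.667/9.5 = 18% (17 of 100 volumes on a 0.1 mL grid starting at 0.1 mL).

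On coarser dose grids the share is higher. With 1, 3, 5, 10 mL it is 9 of 20 volumes (45%) in 0.5 mL steps from 0.5 mL; with 1, 3, 6, 10 mL it is 10 of 19 (53%) in 0.5 mL steps from 1 mL.

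**The plan's sample size (section 3.5).** 30% versus 10%, two-sided 0.05, 80% power: 62 per arm without continuity correction and 72 with it. The stated 72 reproduces.

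**Power with both arms capped.** Let b be the share of doses capped and o the share of errors that are overdoses (assumed 0.5). If every blocked overdose is scored accurate, each error rate is multiplied by 1 − b × o. With p̄ the mean of the two rates, continuity-corrected power at n = 72 is

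Φ{[(|p1 − p2| − 1/n)√n − 1.96√(2p̄(1 − p̄))] / √(p1(1 − p1) + p2(1 − p2))}.

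- No cap, 30% v 10%: (1.579 − 1.109)/0.548 = 0.859; power 80%.
- b = 0.18: 27.3% v 9.1%; power 75%.
- b = 0.33: 25.05% v 8.35%; (1.299 − 1.034)/0.514 = 0.516; power 70%.

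Without continuity correction the uncapped figure at 72 is 86%, and the capped figures are 81% and 77%.

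**False-favourable rate with only the intervention arm capped.** No true effect, 30% true error in both arms, 72 per arm, exact enumeration of the two-sided 5% pooled z test, counting only results that favour the intervention:

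| Capped share | Intervention arm reads | Uncorrected | Continuity corrected |
|---|---|---|---|
| 0 | 30% | 2.5% | 1.6% |
| 0.18 | 27.3% | 5.5% | 4% |
| 0.33 | 25.05% | 10% | 7% |

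**If remainders count as errors.** A pictured second fill more than 20% below the prescription is still an error on the ±20% scale. If half of the blocked overdoses appear that way, then at b = 0.33 power is 75% rather than 70%, and the uncorrected false-favourable rate is about 5% rather than 10%.

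**Comparison of medians.** A simulation used no true effect, 30% errors (half overdoses of 20–100%, half underdoses of 20–80%), 3% measuring noise, sizes 1, 3, 5, 10 mL, evenly spread doses, and the cap in the intervention arm only. The median moved by no more than about 0.03 percentage points, and a two-sided 5% rank-sum test rejected about 5% of the time. The plan names no test for this comparison; rank-sum is an assumption.

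**The case against.** The strongest reply is that the planned primary comparison is of medians, and trimming an upper tail hardly moves a median. This stands: a reader might infer that the primary analysis as a whole is biased, and the simulation does not support that. The ±20% form is still affected, and it carries the sample size, both risk reductions and the number needed to treat.

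Second, every magnitude rests on assumed stock, dose mix and overdose share, and treats all blocked overdoses as accurate. This also stands; the figures are conditional and toward the upper end. The plan calls its 30% control rate conservative. At 40% versus 10% with the same masking (b = 0.33, o = 0.5), power is still about 95%.

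Third, the envelope syringe is there to standardise assessment, which suggests matched sizes. That may be the intention, but the text gives no size. A reader might infer either a definite bias toward the intervention or a definite match; the documents establish neither.

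Fourth, the reported dose is collected in mL, judged at the same 20% limit and not bounded by a syringe. It can catch a caregiver who believes the dose is larger, but it is a separate measure and does not correct the observed dose. The follow-up survey form and Figure 2 are not visible here, so an existing item on fills cannot be ruled out.

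Fifth, the close-fitting syringe belongs to the intervention and may truly prevent single-fill overdoses. Fewer large readings in that arm are therefore not necessarily artefact. One picture cannot separate prevention from an unseen second fill; a count of fills can.

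**Conclusion.** The point holds in a limited form. At least in the intervention arm, a dose at or above about 83% of the syringe's capacity cannot show an overdose above 20% in a single-fill picture, and the described scoring can record a two-fill dose as accurate or as an underdose. This follows from sections 3.3 to 3.5, given only that the syringe is not read past its top mark.

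The size is conditional. Under the assumed sizes, about 17–35% of volumes are capped for evenly spread doses, and up to about half on coarser grids. With 18–33% capped and half of errors overdoses, expect at most about 5 to 10 points of lost power if both arms are capped, or a false-favourable rate of about 5.5–10% (uncorrected; about 4–7% corrected) if only the intervention arm is. Both shrink if pictured remainders are scored as errors.

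Three stronger readings are not supported. The stated 72 per arm is not an error. The 4.5 mL example is not shown to be impossible, since it conflicts with the sizing rule only for certain stocks. Nor can one say how many trial doses are affected.

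The change is still worth making, because the number of fills cannot be recovered from one picture afterwards.

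**What to change.** - Add one myCap item at the time of the picture: how many syringefuls make up this dose?
- Define the observed dose as number of fills times the reading, and state which fill is to be photographed if the last one is partial, so that the product is well defined.
- Code a syringe filled to its last mark as at or above capacity, not as an exact volume.
- State the size of the assessment syringe in each arm and use the same sizing rule in both.
- Say how the 4.5 mL against 3 mL example fits that rule.

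A larger assessment syringe with headroom above the dose is optional. It would let bigger overdoses be read directly, but it would no longer measure any real prevention by the close-fitting syringe, which is part of what is being tested.

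Cost: a short amendment and one extra survey item. The main downside is that the fill count relies on caregiver report, so the observed measure becomes partly self-reported for caregivers who fill more than once.
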